10.2. Informed consent

The investigator must obtain documented consent from each potential subject prior to participating in this study. Consent must be documented by the subject's dated signature or by the subject's legally acceptable representative's dated signature on a consent form along with the dated signature of the person conducting the consent discussion. A copy of the signed and dated informed consent form (ICF) should be given to the subject before participation in the study.

The initial informed consent form and any subsequent revised written informed consent form provided to the subject must receive the favorable opinion from the relevant ethics committee in advance of use. The subject or his/her legally acceptable representative should be informed in a timely manner if new information becomes available that may be relevant to the subject's willingness to continue participation in the study. The communication of this information will be provided and documented via a revised consent form or addendum to the original consent form that captures the subject's dated signature or by the subject's legally acceptable representative's dated signature.

10.3. Personal data protection

The subject's personal data and investigator's personal data which may be included in the Sponsor database will be treated in compliance with Directive 95/46/EC of the European Parliament and of the Council, other applicable laws and regulations.

When archiving or processing personal data pertaining to the investigator and/or to the subjects, the Sponsor will take all appropriate measures to safeguard and prevent access to this data by any unauthorized third party.

The name of the subjects as well as other person-related data must not be forwarded by the investigator to the third party (with exception of regulatory inspectors or auditors or monitors for monitoring purposes). If it is necessary to identify the name of a subject during the course of the study due to medical reasons, the employees of the Sponsor and investigator taking part in the study conduct this under the observance of professional discretion. The investigator takes care that eCRF or other documents assigned to the sponsor do not include the name of the subject. The investigator handles a separate subjects' identification list which allows allocation of subject's identification code to his/her name.

Authorized persons can get access to the medical records in the context of monitoring, audit or inspection. This must be agreed and signed by the subject by signing Informed Consent Form.

11. MANAGEMENT AND REPORTING OF ADVERSE EVENTS/ADVERSE REACTIONS

Safety data will be processed and managed by CRO Biomapas. PcVmanager™ software will be used for this purpose. Serious ADRs will be reported to State Institute for Drug Control of Slovak Republic via EudraVigilance portal within required timelines. Research ethics committees will be notified according the applicable legislation.

Detailed information on the management and reporting of adverse events will be provided in Safety Management Plan.

11.1 Definitions

11.1.1 Adverse event

According to the ICH guideline for Good Clinical Practice, an adverse event (AE) is any untoward medical occurrence in a patient or clinical investigation subject administered a pharmaceutical product and which does not necessarily have to have a causal relationship with this treatment. An adverse event can therefore be any unfavorable and unintended sign (including an abnormal laboratory finding), symptom, or disease temporally associated with the use of an investigational product, whether or not considered related to the medicinal product.

Adverse events associated with the use of a medicinal product in humans, whether or not considered related, include the following:

- an adverse event occurring in the course of the use of a medicinal product in professional practice,
- an adverse event occurring from an overdose whether accidental or intentional,
- an adverse event occurring from medicinal product abuse,

- an adverse event occurring from medicinal product misuse,
- an adverse event occurring from medicinal product withdrawal,
- an adverse event occurring from medicinal product off-label use,
- an adverse event occurring from occupational exposure,
- an adverse events where there is a reasonable possibility that the event occurred purely as a result of the subjects participation in the study (e.g., adverse event or serious adverse event due to discontinuation of other medicinal products during wash-out phase) must also be reported as an adverse event even if it not related to the investigational product.

11.1.2 Special situations

In addition to AEs, the following special situations will be of interest, whether associated with AE or not:

- accidental or intentional overdose,
- medicinal product abuse or misuse,
- medication errors,
- medicinal product off-label use,
- pregnancy or breastfeeding exposure,
- lack of therapeutic efficacy,
- product quality complaints.

11.1.3 Serious adverse event

A serious adverse event (SAE) as defined by ICH as any untoward medical occurrence that at any dose meets any of the following conditions:

- results in death,
- is life-threatening,
- requires inpatient hospitalisation or prolongation of existing hospitalisation,
- results in persistent or significant disability/incapacity,
- is a congenital anomaly/birth defect, or
- is an important medical event.

Life-threatening: the term “life-threatening” in the definition of serious refers to an adverse event in which the subject was at risk of death at the time of the event. It does not refer to an adverse event which hypothetically might have caused death if it were more severe.

Hospitalisation: any adverse event leading to hospitalisation (inpatient admission or overnight stay) or prolongation of hospitalisation will be considered as serious, UNLESS at least one of the following exceptions is met:

- the admission is pre-planned (i.e., elective or scheduled surgery arranged prior to the start of the study), OR
- the admission is not associated with an adverse event (e.g., social hospitalisation for purposes of respite care).

Important medical event: any adverse event may be considered serious based on medical and scientific judgment because it may jeopardise the subject and may require intervention to prevent one of the outcomes listed in the definition above. Any adverse event is considered a serious

adverse event if it is associated with clinical signs or symptoms judged by the investigator to have a significant clinical impact.

A suspected transmission of infectious agent via a medicinal product must also be considered as a serious adverse event.

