9.3.2. Safety variables

Safety variables include:

- proportion of subjects with adverse renal effects (as defined in Section 9.3.1)
- proportion of subjects, who experienced any AE;
- proportion of subjects with ADRs;
- proportion of subjects experiencing serious adverse events (SAEs);
- proportion of subjects with serious ADRs;
- severity of AEs;

- number of subjects who discontinued the study and the reasons for drop-outs;
- global assessment of tolerability by investigators: very good (no intolerance reactions), good (occasional intolerance reactions), moderate (frequent intolerance reactions), poor (intolerance reactions after every use);
- global assessment of tolerability by subjects: very good, good, moderate and poor.

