11.2.1 Assessment of severity of adverse event

Severity of adverse events should be graded as follows:

- Mild – usually transient in nature and generally not interfering with patient’s normal activities;
- Moderate – sufficiently discomforting to interfere with patient’s normal activities;
- Severe – prevents patient’s normal activities.

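### In section 11.1.3 the last sentence on important medical events is broader than the definition it explains, and may inflate the SAE and serious-ADR proportions

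*Protocol*

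**What the plan says.** Section 11.1.3 of the protocol attributes its SAE definition to ICH: "any untoward medical occurrence that at any dose meets any of the following conditions". Six conditions follow. Five are death, threat to life, hospitalisation, disability and congenital anomaly. The sixth is that the event "is an important medical event".

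The paragraph explaining the sixth condition has two sentences. The first says that an event may be considered serious on medical and scientific judgement, "because it may jeopardise the subject and may require intervention to prevent one of the outcomes listed in the definition above". The second begins "Any adverse event is considered a serious" and continues "adverse event if it is associated with clinical signs or symptoms judged by the investigator to have a significant clinical impact".

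Other sections depend on this wording:

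- Section 11.2 sends the investigator to 11.1.3 to judge seriousness and, separately, to 11.2.1 to grade severity. The top grade there is "Severe – prevents patient’s normal activities".
- Section 9.3.2 lists the proportion of subjects with SAEs and the "proportion of subjects with serious ADRs" among the safety variables.
- Section 11.3 requires SAEs to reach the CRO within 24 hours. Section 11.4 requires those assessed as related to reach the national authority within 15 calendar days.

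**The concern.** The two sentences give an investigator two different tests for the same criterion. An event with troublesome symptoms, but no prospect of leading to any listed outcome, is not serious under the first. It is serious under the second if the investigator thinks its clinical impact significant. Nothing in the protocol says which sentence governs or what counts as significant.

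At stake are two listed safety variables and the volume of expedited reports. The SAE and serious-ADR proportions may rise because of wording rather than because of the drug. They may also differ between sites according to which sentence each investigator follows. The protocol expects about 15 sites (section 9.2). The independent adjudication it describes covers suspected renal effects only (section 9.3.1), so for other events the proportions rest on the investigator's classification.

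**Working it through.** **Step 1. The two sentences side by side (section 11.1.3).**

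| Element | First sentence | Second sentence |
|---|---|---|
| Force | may be considered serious | is considered serious |
| Events covered | any adverse event, on medical and scientific judgement | any adverse event |
| Test | possible jeopardy to the subject and possible need for intervention | signs or symptoms with significant clinical impact |
| Link to a listed outcome | yes, intervention to prevent one | none |
| Key term defined | tied to the list above it | not defined anywhere |

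The second sentence states a complete condition of its own and does not refer back to the first. Any event that meets its test but not the first sentence's is therefore serious on one reading and non-serious on the other.

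**Step 2. Is the difference only verbal?** The same section takes care over this boundary elsewhere. Its note on life-threatening events excludes those that could have been fatal only had they been more severe. The second sentence on important medical events contains no such limit.

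**Step 3. Where the classification goes.** From 11.1.3 it passes through 11.2 to the two variables in 9.3.2 and to the reporting in 11.3 and 11.4. An event judged related is an ADR under 11.2.2, so a related event made serious by the second sentence becomes a serious ADR.

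**Step 4. What can be computed.** The protocol states no figure on this point and makes no sample size calculation (section 9.5), so there is nothing to reproduce. The planned number of subjects is n = 500 (section 9.5). The number x of subjects who become cases only through the second sentence is not given. It is an assumption, shown here from 0 to 10.

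- Proportion = x/n, so each such subject adds 1/500 = 0.2 percentage points.
- Exact (Clopper-Pearson) 95% limits: the lower is the 0.025 quantile of Beta(x, n − x + 1), taken as 0 when x = 0. The upper is the 0.975 quantile of Beta(x + 1, n − x).

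| x | x/500 | Exact 95% CI |
|---|---|---|
| 0 | 0.0% | 0 to 0.735% |
| 1 | 0.2% | 0.005% to 1.109% |
| 5 | 1.0% | 0.325% to 2.318% |
| 10 | 2.0% | 0.963% to 3.647% |

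**Step 5. Reading the table against the SmPC.** Section 4.8 of the annexed SmPC says that no serious adverse reactions have been reported. It puts uncommon at 1/1,000 to below 1/100 and common at 1/100 to below 1/10. If the reclassified events are also judged related and there are no other serious ADRs, one subject (0.2%) gives a point estimate in the uncommon band. Five (1.0%) give one at the lower edge of the common band. Unrelated events raise the SAE proportion but have no bearing on the SmPC statement.

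**The case against.** The strongest reply is that this is loose wording inside a paragraph whose subject is clear. The sentence sits under important medical events, directly after a reference to medical judgement, and can be read as a gloss on that criterion. That reading is available. The sentence does not require it, however, and a definition open to two readings needs reconciling whichever was intended.

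Two stronger conclusions that a reader might draw are not supported:

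- **That the sentence contradicts an outcome-based definition.** The list is not purely outcome-based, because its sixth condition already rests on judgement. The defect is an inconsistent broadening of that condition.
- **That the SAE count will consist partly of merely severe events.** Severity in 11.2.1 turns on normal activities and the disputed sentence on clinical impact. Neither implies the other, and 11.2 still asks for separate assessments. Intensity may influence the seriousness judgement, but the text does not equate the two.

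Other parts of the reply also stand:

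- The primary objectives are not affected. ADRs count whether serious or not, and suspected renal effects are adjudicated.
- The study is descriptive, so no hypothesis or threshold turns on these two proportions. No comparison with the SmPC statement is planned.
- Any error is towards over-reporting, and 11.4 foresees that a case may become non-serious on follow-up.
- The fields of the SAE form and the content of the Safety Management Plan are not shown, so no gap in them can be inferred.

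These points limit the consequences. They do not remove the mismatch between the two sentences.

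**Conclusion.** The point holds as an internal inconsistency in a stated rule. The last sentence of the important-medical-event paragraph is wider than the definition it explains. It may raise the SAE and serious-ADR proportions, make them depend on the investigator's reading, and bring events that meet none of the six conditions, as the first sentence explains them, into 24-hour and 15-day reporting.

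Its size cannot be derived from the document. Each subject who is a case only through this sentence adds 0.2 percentage points. This assumes that all 500 planned subjects are dosed, and so enter the safety analysis, and that the subject has no other qualifying event. A handful of such subjects would matter for the serious-ADR proportion only if their events were also judged related. The two primary objectives are untouched.

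**What to change.** Reconcile the two sentences in section 11.1.3. Either delete the second, or make it expressly subject to the test in the first, in the protocol's own terms: "it may jeopardise the subject and may require intervention to prevent one of the outcomes listed in the definition above". Keep the word that joins the two parts of that test. Replacing it with an alternative would create a third, wider definition.

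The cost is one sentence in the protocol. Slightly fewer events would be classed as serious and go through expedited reporting. No event is lost: section 11.2 requires every adverse event to be recorded whatever its severity, and section 9.3.2 reports severity as a separate variable.

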11.2 Recording of adverse events

During the study subjects must be carefully monitored for adverse events or special situations and the investigator will be responsible for the determination and documentation of them. Adverse events should be assessed in terms of their seriousness, severity and relationship to Polyoxidonium.

Adverse events will be determined in one of the three ways:

- observed by the investigator;
- identified by general questions about any changes in subjects well-being, asked at all study visits;
- spontaneously reported by the subjects to the investigator.

The investigator is responsible for ensuring that all AEs, irrespective of its severity, intensity, and suspected relationship to Polyoxidonium, are recorded in the subject's medical record and on the eCRF.

For each AE recorded on the eCRF, the investigator will make an assessment of seriousness (see Section 11.1.3 for seriousness criteria), severity (see Section 11.2.1), and causality (see Section 11.2.2). All measures, taken to treat adverse event, must be described in medical documentation.

After informed consent has been obtained, all adverse events, regardless of relationship to Polyoxidonium, will be reported until study closure. Any AE that is still ongoing at the completion/discontinuation visit will have an outcome of „ongoing“ in the eCRF, whereas the investigator will continue to follow up ongoing AEs and record information in the subjects medical documents. SAEs will be followed until the event resolves or the event or sequelae stabilise and this information will be reported to the Sponsor.

The investigator does not need to actively monitor subjects for adverse events once the study has ended. However, if becoming aware of any serious adverse events occurring to a subject within 30 calendar days after subject completed or withdrew the study, the investigator should report those to the Sponsor.

For all adverse events, a diagnosis (if known) should be recorded on the eCRF rather than individual signs and symptoms (e.g. record only liver failure or hepatitis rather than jaundice and elevated transaminases). However, if a constellation of signs and/or symptoms cannot be medically characterized as a single diagnosis or syndrome at the time of reporting, each individual event should be recorded on the eCRF. If a diagnosis is subsequently established, all previously reported adverse events based on signs and symptoms should be nullified and replaced by one adverse event report based on the single diagnosis, with a starting date that corresponds to the starting date of the first symptom of the eventual diagnosis.

11.2.1 Assessment of severity of adverse event

Severity of adverse events should be graded as follows:

- Mild – usually transient in nature and generally not interfering with patient’s normal activities;
- Moderate – sufficiently discomforting to interfere with patient’s normal activities;
- Severe – prevents patient’s normal activities.

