9.3.1. Definition of event of interest

In case of suspected adverse renal effect investigator will be encouraged to apply clinical judgement, to perform diagnostic workup and collect as much data as possible to confirm or reject the diagnosis of renal impairment. The signs and symptoms of renal toxicity, indicative of potential renal impairment include but are not limited to: increased blood concentrations of creatinine, potassium, blood urea nitrogen, urine protein levels, ECG changes, characteristic to elevated potassium levels; symptoms of intoxication, e.g. fatigue, nausea, vomiting.

These data for each subject for whom adverse renal effect is suspected will be reviewed and adjudicated by an independent assessor. This final adjudicated conclusion will be qualified as event of interest (a case of adverse renal effect) or suspicion about renal toxicity will be rejected.

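### The severity scale has no criterion for laboratory findings, so a symptom-free laboratory adverse event, renal ones included, can be graded no higher than mild whatever its magnitude

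*Protocol*

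**What the plan says.** Protocol section 11.2.1 gives a single scale:

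- Mild: "usually transient in nature and generally not interfering with" normal activities.
- Moderate: "sufficiently discomforting to interfere with" them.
- Severe: "Severe – prevents" them.

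Section 11.2 applies the scale to every event: "For each AE recorded on the eCRF, the investigator will make an assessment of seriousness", and the same sentence adds severity, with a pointer to 11.2.1, and causality. Section 11.1.1 counts as an adverse event "any unfavorable and unintended sign (including an abnormal laboratory finding), symptom, or disease" in temporal association with the product.

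Section 9.3.1 begins its open-ended list of renal signs with "increased blood concentrations of creatinine, potassium, blood urea nitrogen, urine protein levels". It then adds potassium-related ECG changes and symptoms such as fatigue, nausea and vomiting. Section 9.3.2 lists "severity of AEs" among the safety variables. The protocol contains no laboratory-based grading.

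**The concern.** The study exists because animal work pointed to the kidney. That evidence, as told in section 7.2, was biochemical and histological: raised serum creatinine and urea, with glomerular and tubular changes. Four of the signs named in 9.3.1 are likewise laboratory measurements. A severity scale that asks only about discomfort and activities carries no information on the size of such a change when the subject feels well.

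What is at stake is the meaning of the severity summary. For symptom-free laboratory events, small and large departures share a grade, and the loss runs in the reassuring direction. The grade is an investigator judgement made during the study under a rule fixed in the protocol. An analysis plan can add laboratory summaries later, but it cannot make the recorded grades informative.

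**Working it through.** No sample size, rate or test enters this point, so the check is to apply the rule as written.

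**Step 1: does the scale cover laboratory findings?** Section 11.1.1 makes an abnormal laboratory finding an adverse event. Section 11.2 requires a severity assessment for each recorded event and refers to 11.2.1. So it does.

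**Step 2: which grade can a symptom-free laboratory event meet?**

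| Grade | What 11.2.1 requires | Symptom-free laboratory event |
|---|---|---|
| Mild | Usually transient, generally no interference | Meets the interference part; meets the transience part only if the change is short-lived |
| Moderate | Discomfort enough to interfere | Not met |
| Severe | Activities prevented | Not met |

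Mild is the only grade left. It fits a brief abnormality. It fits a persistent one poorly, and the protocol offers the rater nothing better.

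**Step 3: does magnitude alter the result?** Take two subjects without symptoms, one at 1.1 times and one at 3 times the upper reference limit for creatinine (illustrative values, not from the protocol). Neither figure enters any grade definition, so both subjects land on mild. A third subject with brief nausea that disturbs the day is graded moderate.

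**Step 4: does another rule supply the missing degree?**

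- *Adjudication (9.3.1)* returns a case or a rejection, without a degree.
- *Seriousness (11.1.3, 11.3)* can flag a large abnormality through medical judgement, and laboratory abnormalities are expressly covered. It is a yes/no attribute: it does not rank non-serious events, and a serious symptom-free laboratory event would still be graded mild.
- *Recording a diagnosis in place of signs (11.2)* changes the term, not the scale.

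**Step 5: where is the grade used?** Section 9.3.2 lists nine safety variables, and one of them is severity. The renal proportion in that list follows the adjudicated definition in 9.3.1. The stratified analysis and logistic regression in 9.7.1 concern whether a renal effect occurred. The protocol gives the grade no role in any of these.

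**The case against.** The strongest reply is that little depends on the grade. The main renal result is an adjudicated proportion. Clinically important abnormalities can be declared serious without any activity criterion, and serious events have their own lines in 9.3.2. Laboratory results obtained in routine practice are entered in the eCRF (9.3), so magnitude is not lost to the study, and showing peak values could be left to the analysis plan. All of this stands, and it limits the point to the severity variable. It does not answer the point, because none of these routes gives a usable grade to a non-serious, symptom-free laboratory event.

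Three stronger readings are tempting, and the documents do not support them:

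- *Renal events are usually symptom-free and so will be graded mild.* The protocol does not say how often they are symptom-free. Section 9.3.1 names symptoms among the renal signs, and a case with such symptoms can be graded moderate or severe.
- *The scale rests on interference alone.* Mild also refers to transience and moderate to discomfort. That wording is why a persistent symptom-free change has no clean place on the scale.
- *The renal severity table could read 100% mild.* No such table is planned. If renal cases fell in the uncommon band of section 9.5 (an assumption), 500 subjects would give 500 × 1/1000 = 0.5 to 500 × 1/100 = 5 cases. A severity distribution over so few cases says little on any scale, and section 9.7 allows presentations to be dropped when data are sparse. The result would also need every case to be symptom-free.

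**Conclusion.** The point holds in limited form. As written, 11.2.1 cannot grade a symptom-free laboratory adverse event above mild, and it has no proper grade for a persistent one. The conclusion follows from the wording and rests on two conditions: the finding is recorded as an adverse event, and the investigator applies the scale literally. An investigator might in practice grade by clinical impression, but the protocol gives no basis for doing so consistently.

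The consequence is an uninformative grade for one class of event within one descriptive variable. Its numerical size cannot be stated, because the documents do not give the share of symptom-free laboratory events. A reader might infer that the study cannot tell trivial from major renal changes at all. That goes too far, since adjudication, the seriousness assessment and the recorded laboratory values all remain. This is a worthwhile improvement and not a threat to the primary objectives.

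**What to change.** Add to section 11.2.1 that an adverse event consisting of a laboratory finding without symptoms is graded by magnitude. The comparison is with the subject's own baseline or, where no baseline was recorded, with the reference limit. Use one published laboratory toxicity scale, chosen by the sponsor and fixed before the first subject is enrolled. Keep the activity-based scale for symptomatic events and for ECG findings. List the peak laboratory value beside each adjudicated renal case.

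The fallback to the reference limit is needed because results are recorded only if obtained in routine practice, within 3 days before enrolment or during the study (Table 1 and 9.3), so some subjects will have no baseline. ECG findings stay on the existing scale because 9.3 records ECG abnormalities and not measurements; the limitation therefore remains for symptom-free ECG findings.

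The cost is one paragraph and one eCRF field. No test, visit or treatment is added, so the non-interventional design is unchanged. The drawbacks are that the adverse event tables must show two grading scales, clearly labelled, and that grading by magnitude is possible only where routine laboratory values exist.
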